NCT03544515

Title: Treatment of peri-implantitis: clinical comparison between conventional treatment versus conventional plus Biolase laser treatment as a co-adjuvant

Protocol: AAAR8727

Principal Investigator: [name], [name]

IRB Approved Effective Date: 02/23/2022

Study Purpose and Rationale

With advances to implant dentistry over the past several decades, endosseous implants have become more prevalent in the population as an effective means of restoring function to edentulous areas. The use of dental implants has transformed the dental landscape and has dramatically altered the way clinicians treat edentulous and partially edentulous patients. As the number of implants is on the rise, the prevalence of disease around existing dental implants has become more widespread. Peri-implantitis has been defined as the presence of destructive soft tissue inflammation leading to pocket formation and bone loss around an osseointegrated implant (Albrektsson T, 1994). The presence of peri-implantitis has been estimated to be between 28-56% of patients and 12-40% of implants (Zitzmann N, 2008). The widespread presence of peri-implantitis has led to numerous attempts to manage and treat a disease which currently has no standardized protocol. Many methods at attempting to control the inflammatory process around implants have been attempted. In cases of peri-mucositis in animal studies, non-surgical therapy utilizing mechanical debridement has been shown to reduce inflammation (Trejo P, 2006). Non-surgical debridement of the implant is often the first line of defense, along with oral hygiene instruction, to prevent cases of peri-mucositis to progress to pocket formation and bone loss. Chlorhexidine rinses (Felo A, 1997) and both systemic (Mombelli A, 1992) and local (Büchter A, 2004) treatment with antibiotics have also been used as adjunctive therapy with varying results. Non-surgical therapy of peri-implantitis cases has not shown, however, to produce predictable results in terms of pocket reduction and reduced inflammation in the long term (Renvert S, 2008). Eventually, surgical intervention for cases of significant pocketing was also attempted around dental implants. The Cumulative Interceptive Supportive Therapy (CIST) protocol was developed out of these previous findings.

Systematic reviewers have suggested that combining several non-surgical therapies together for mild cases and surgical intervention for severe cases appears to be the most effective method of approaching peri-implantitis (Klinge B, 2002). The CIST protocol recommends mechanical debridement for cases with no attachment loss around an implant, which are essentially mucositis cases. When pocket depths approach 4-5 mm, antiseptic cleansing is recommended as an addition to mechanical debridement. When minor bone loss of less than 2 mm is detected as well, systemic or local antibiotic therapy is then administered. When the amount of bone loss exceeds 2 mm, the protocol then recommends resective or regenerative surgery in the site (Lang N, 2004). Relatively recently, the use of lasers for treatment of peri-implantitis has shown promising results across a variety of laser systems. Various authors have published cases utilizing CO₂, diode, Er,Cr:YSGG, Er:YAG, and Nd:YAG lasers to treat peri-implantitis. Currently, the use of lasers provides a mean to remove the bacterial challenge on the surface of titanium implants. Er,Cr:YSGG in peri-implantitis cases has shown reduced pocket depths and bleeding on probing (Al-Falaki R, 2014). In another case report, Er,Cr:YSGG has improved pocket depth, bleeding, implant mobility, and bone formation around implant (Azeeh M, 2008). Er,Cr:YSGG seems efficient in removing contaminants on roughened implant surface with no effects on titanium substrate under electronic microscope examination (Miller R, 2004). Schwarz has several studies using the Er:YAG laser and have shown that decontamination of the implant surface is possible through his methods as well, although there is no definitive protocol and efficacy of its usage (Schwarz F, 2006). Furthermore, in a study using diode lasers for the treatment of peri-implantitis, Lerario showed a significant reduction in probing depth in patients treated with a diode laser compared to those treated with standard scaling and root planing (Lerario F, 2016) while one formation was evident in one peri-implantitis case treated with Er,Cr:YSGG (Zuhair S, 2015). These promising results promote the need to conduct additional studies that elucidate the efficacy of utilizing lasers in the treatment of peri-implantitis as very few studies have been shown comparing the use of lasers as a means to sanitize the surface of the implant in comparison

to other methods in a randomized, controlled environment. As mentioned, previous studies verify that decontamination of the implant surface is very successful with the use of lasers, and this area of implant dentistry warrants further exploration. The aim of this study is to explore the clinical effects of treating ailing implants non-surgically with the Er,Cr:YSGG laser, and compare the results to traditional methods of non-surgical therapy.


Study Design

This clinical study will involve 26 human subjects pre-screened at Columbia University with the presence of at least one implant presenting with early to moderate peri-implantitis. Peri-implantitis has been defined as an implant restoration with inflamed bleeding gingiva, probing depths around the implant of 5- 8mm, bone loss and exposure of threads around the implant (limited to one-third of the threads exposed). The purpose of this study is to determine the benefits of treating peri-implantitis with a closed laser approach known as the "Repair Protocol" using an Er,Cr:YSGG laser compared with traditional non-surgical therapy. Each subject, when determined to fall under the parameters of the study for peri-implantitis, will be randomly assigned to one of two groups: the test Er,Cr:YSGG laser group or the control group. The study will constitute a human double-blind randomized clinical trial in which both examiners and patients will be blinded to the treatment. In order to ensure the blinding of the patients, the laser will be applied to all implants, although it will not be activated in the control group. The therapist will be the same person throughout the study while the examiners will be calibrated. The two groups that will constitute the study and the procedures that will be applied are:

Experimental: Scaling and root planning with an ultrasonic or piezoelectric instrument and hand instrumentation with hand instruments. No prosthetic components will be removed. Application of laser therapy following the specifics of the company.

Control: Scaling and root planning with an ultrasonic or piezoelectric instrument and hand instrumentation with hand instruments. A sham, inactivated laser, treatment will be delivered.

Data to be collected include: Primary outcome measures will include: presence of bleeding on probing, probing depth, and the progression of bone loss around the implant, as measured with bone sounding under local anesthesia and radiographically with the aid of a stent. Secondary outcome measures will include: Gingival index (GI), Plaque Index, mobility, and suppuration.

Statistical Procedures

Power calculation was done based on a study published by Lerario et al., 2016. To detect a difference of 1.72 mm (SD: 1.13mm) in probing depth at 9 months of follow-up after the use of Er,Cr: YSGG laser therapy we will need 13 patients in each of control and test groups (at 90% power, and alpha of 0.05). The ratio of sample size in group 1 to group 2 is 1.

Confidentiality

The study data will be recorded on paper during the appointments and will be transferred electronically to an encrypted computer designated for the study. The paper copy will only be seen and handled by the primary provider. When the data is transferred electronically, the hard copy will be destroyed. The excel files will only be located on encrypted laptops and desktops designated for the study. The data will be coded once it becomes electronic, and only the study team will have access to the identifiable data.

Limitations of compelled disclosure and mandatory reporting apply, and only during these special circumstances will the identities be disclosed.

Participants will only be seen by faculty and students participating in the study. During analysis of the data, patients will not be identified by name, only by a designated number identifying the patient in the health record software (coded). Only members of the study team will have access to the identifiable data.

Study Procedures

On the day of treatment, each subject will be randomly assigned to either the control group or the treatment group (envelopes with the respective groups will be prepared and drawn at the day of treatment). All ailing implants will be left closed with no incisions or flaps made to expose the implant surface surgically. Prior to treatment, radiographs will be taken utilizing a radiographic stent utilizing bite registration impression material, which will be stored for the final radiograph at the end of the study for standardization. In addition, gingival bleeding, recession, loss of attachment and tissue type will be recorded. All subjects receiving treatment will then be anesthetized with 2% lidocaine with 1:100,000 epinephrine, utilizing only buccal and palatal infiltrations with no interpapillary injections. The implant will be sounded with a periodontal probe to measure bone levels at four sites.

In the control group, the implants will be debrided with curettes and ultrasonic scaler with standard tips. No prosthetic components will be removed in this study. The occlusion of the restorations supported by the ailing implant will be evaluated, and all balancing contacts, heavy occlusion, and excessive marginal ridge contacts will be removed.

In the Er,Cr:YSGG laser test group, the Er,Cr:YSGG laser will then be used to irradiate the implant surface utilizing a closed technique. The "Repair Protocol" will be utilized on the experimental implants. The "Repair Protocol" consists of several steps including but not limited to the following: Outer Pocket De-Epithelialization, Gingivectomy (as needed), De-Epithelialization and Retraction, Scaling and Root planing, Sulcular Debridement/Degranulation, Bone Decortication, Final Sulcular Debridement, and Compression with a wet 2X2. Occlusal adjustment will also be done at the conclusion of the procedure identical to the control group.

Oral hygiene instructions will be given to all patients after treatment.

Subjects will return for 1-week, 3-month, 6-month & 9-month evaluations. At the initial and the 9-month visits, the implant will be assessed for bleeding on probing, probing depths at four sites around the implant, clinical attachment level, and recession. Standardized radiographs will be taken at baseline and at the end of study at 9 months. At every recall visit, only supragingival polishing will be completed without the use of curettes or periodontal probes. At 9 months, the patient will receive a final evaluation for the study.

Medical Device

Device name: WaterLase iPlus

Device description: Er, Cr:YSGG laser

Device Model/Version #: WaterLase iPlus

Phase of Study: Feasibility

Manufacturer: Biolase Technology, Inc.

Recruitment

Participants will be currently enrolled patients being seen at Columbia University College of Dental Medicine. Patients at Columbia University will have already completed written consent to be treated at the University for dental care. Participants of the study will be approached by their current dental provider and if they agree, then they will be brought into contact with the research team. Alternatively, the treating dentist may provide information about the study along with contact information for the researchers, so the patients may contact the researchers if they are interested in participating. If the patient shows interest, he or she will have an interview with the Principal Investigator or other investigators to discuss the details of patient involvement and the potential risk and complications derived from the participation in the study. Written consent will be obtained prior to treatment and induction into the study on a day prior to rendering treatment for the study itself.

Research Question(s)/Hypothesis(es)

The purpose of the study is to observe the effects of two commonly utilized treatment modalities for peri-implantitis and to compare the results. The first method of treatment is debridement with curettes and ultrasonic scalers and it represents the traditional approach in the treatment of peri-implantitis. The

second method of treatment involves the use of the Biolase laser in addition to the traditional approach of debriding with curettes and ultrasonic scalers. No studies exist comparing these two approaches, and this will serve as a pilot study to explore possible differences. Our research hypothesis is that the addition of Er,Cr:YSGG laser is likely to be more effective in removing the microbiota from a rough implant surface, and that this will manifest with improved clinical parameters in subjects that receive this method of treatment.

Scientific Abstract

With advances to implant dentistry over the past several decades, endosseous implants have become more prevalent in the population as an effective means of restoring function to edentulous areas. The use of dental implants has transformed the dental landscape and has dramatically altered the way clinicians treat edentulous and partially edentulous patients. As the number of implants is on the rise, the prevalence of disease around existing dental implants has become more widespread. Peri-implantitis has been defined as the presence of destructive soft tissue inflammation leading to pocket formation and bone loss around an osseointegrated implant (Albrektsson T, 1994). The presence of peri-implantitis has been estimated to be between 28-56% of patients and 12-40% of implants (Zitzmann N, 2008). The widespread presence of peri-implantitis has led to numerous attempts to manage and treat a disease which currently has no standardized protocol. Many methods at attempting to control the inflammatory process around implants have been attempted. In cases of peri-mucositis in animal studies, non-surgical therapy utilizing mechanical debridement has been shown to reduce inflammation (Trejo P, 2006). Non-surgical debridement of the implant is often the first line of defense, along with oral hygiene instruction, to prevent cases of peri-mucositis to progress to pocket formation and bone loss. Chlorhexidine rinses (Felo A, 1997) and both systemic (Mombelli A, 1992) and local (Büchter A, 2004) treatment with antibiotics have also been used as adjunctive therapy with varying results. Non-surgical therapy of peri-implantitis cases has not shown, however, to produce predictable results in terms of pocket reduction and reduced inflammation in the long term (Renvert S, 2008). Eventually, surgical intervention for cases of significant pocketing was also attempted around dental implants. The Cumulative Interceptive Supportive Therapy (CIST) protocol was developed out of these previous findings. Systematic reviewers have suggested that combining several non-surgical therapies together for mild cases and surgical intervention for severe cases appears to be the most effective method of approaching peri-implantitis (Klinge B, 2002). The CIST protocol recommends mechanical debridement for cases with no attachment loss around an implant, which are essentially mucositis cases. When pocket depths approach 4-5 mm, antiseptic cleansing is recommended as an addition to mechanical debridement. When minor bone loss of less than 2 mm is detected as well, systemic or local antibiotic therapy is then administered. When the amount of bone loss exceeds 2 mm, the protocol then recommends respective or regenerative surgery in the site (Lang N, 2004). Relatively recently, the use of lasers for treatment of peri-implantitis has shown promising results across a variety of laser systems. Various authors have published cases utilizing Er,Cr:YSGG, Er:YAG, Nd:YAG, and CO₂ lasers to treat peri-implantitis. Currently, the use of lasers provides a means to remove the bacterial challenge on the surface of titanium implants. Er,Cr:YSGG in peri-implantitis cases has shown reduced pocket depths and bleeding on probing (Al-Falaki R, 2014). In another case report, Er,Cr:YSGG has improved pocket depth, bleeding, implant mobility, and bone formation around implants (Azeeh M, 2008). The Er,Cr:YSGG seems efficient in removing contaminants on roughened implant surface with no effects on titanium substrate under electronic microscope examination (Miller R, 2004, Linden E, 2017 to be published). Bone formation was evident in one peri-implantitis case treated with Er,Cr:YSGG (Zuhair S, 2015). Schwarz has several studies using the Er:YAG laser and have shown that decontamination of the implant surface is possible through his methods as well, although there is no definitive protocol and efficacy of its usage

(Schwarz F, 2006) .Very few studies have been shown comparing the use of lasers as a means to sanitize the surface of the implant in comparison to other methods in a randomized, controlled environment. Previous studies verify that decontamination of the implant surface is very successful with the use of lasers, and this area of implant dentistry warrants further exploration. The aim of this study will be to explore the clinical effects of treating ailing implants non-surgically with the Er,Cr:YSGG laser, and compare the results to traditional methods of non-surgical therapy utilizing scalers and chlorhexidine rinses. This experiment will involve 26 human subjects pre-screened at Columbia University with the presence of peri-implantitis, which has been defined as an implant restoration with inflamed bleeding gingiva, bone loss and exposure of threads around the implant. This human clinical trial will utilize early to moderate peri-implantitis with no more than one third of threads exposed. The purpose of this study is to determine the benefits of treating peri-implantitis with a closed laser approach known as the "Repair Protocol" using an Er,Cr:YSGG laser compared with traditional non-surgical therapy. Each subject, when determined to fall under the parameters of the study for peri-implantitis, will be randomly assigned to one of two groups: the test Er,Cr:YSGG laser group or the control group. Primary outcome measures will be the presence of bleeding on probing, gingival index and the progression of bone loss around the implant, as measured with bone sounding under local anesthesia and radiographically with the aid of a standardized stent.

Lay Abstract

Dental implants are becoming more and more popular as a means to replace missing teeth. As more dental implants are being placed each year, clinicians are facing the challenges of common causes for failure or compromise of these dental implants. Gum disease, which has plagued natural teeth for many years, can manifest on dental implants in the form of a disease known as peri-implantitis. Peri-implantitis occurs when the presence of bacteria leads to inflammation of the area, and can be the reason for loss of bone around implants. Currently, there is no standard method for treating peri-implantitis. There are several common methods for treating this disease. One method involves cleaning off the implant with scalers in a manner similar to teeth during cleanings. The other method utilizes the same method and adds the use of a laser to remove most of the bacteria from the surface of the implant. In this study, we would like to compare these two methods and see if there is any additional benefit from using the laser technology. The goal is to determine which method is more effective at arresting the progression of peri-implantitis. For this means, we will be taking clinical measurements and X-rays. This will allow us to determine the status of the implant, improvement in the inflammation and changes in bone level. The implants will be treated at the baseline and checked during the follow-up appointments with the last appointment provided at the 9 months.

Risks, Benefits, Alternatives

The risk involved with the laser debridement directly to the patient is minimal. Potential risks may be postoperative infection or soft tissue trauma. The procedure is a conservative surgery-free debridement of the implant with the Biolase laser, and there is very little risk of having postoperative complications. Proper protocol for laser safety will be followed when utilizing the Biolase laser. Both procedures involved with the study are the standard of care for treatment.

Risks and complications of the use of lasers involve: eye and skin damage, thermal damage of the tissues and the adjacent structures, alterations of the implant, restorations of other surfaces, damage of critical structures (i.e. nerves and vessels), embolism, water splashing and rupture of the tip of the laser.

The benefits of the study with enrolled patients is that they are able to receive treatment on ailing implants, whether through non-surgical means or with use of the laser. There is no compensation for the study, since it utilizes therapy that the patient would have needed regardless of participation. Currently, because no standardized protocol exists for the treatment of peri-implantitis, the benefit of this study will be to help collect data on treatment methods to gain additional knowledge on the most optimal treatment methods for peri-implantitis. This is an area that has very little conclusive evidence in terms of treatment modalities that are most effective, and more information is needed to determine the most effective way to treat peri-implantitis.

The alternative intervention for the subject is to not participate in the study and have the implant treated outside the study.

Data and Safety Monitoring

The data will be recorded on paper when the patient is seen by the operator. The study data will then be stored in an Excel file on an encrypted desktop or laptop computer immediately after the encounter with the patient. The paper documents used to collect data will then be destroyed once recorded electronically. There is minimal risk, and therefore there will be no data and safety monitoring board involved. The measurements will also be recorded in the electronic database for every patient (Axium) as a part of their dental treatment records.

The readings for gingival bleeding, periodontal probing, and attachment loss will be monitored for each patient at every visit and compared with previous readings for every patient. Monitoring for any unexpected outcomes, such as a severe increase in attachment loss/probing or gingival inflammation, will be completed after every visit with a patient for study purposes. Any patient showing aberrant findings and potential high risk for the study treatment will be identified and reported to the IRB. All investigators will be tasked with the data and safety monitoring for all patients.

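### No analysis model is stated, so baseline probing depth has no stated role in the 9-month comparison; adjusting for it by ANCOVA would probably narrow the interval, at a cost of one degree of freedom

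*Combined protocol and SAP*

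**What the plan says.** Statistical Procedures consists of a power calculation and nothing else. The trial is sized "To detect a difference of 1.72 mm (SD: 1.13mm) in probing depth at 9 months of follow-up", and from this "we will need 13 patients in each of control and test groups", at 90% power and alpha 0.05. No test, model, covariate, change score or per-patient summary is given for any outcome.

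Baseline depth is collected. Study Procedures states: "At the initial and the 9-month visits, the implant will be assessed for bleeding on probing, probing depths at four sites around the implant". It adds, for bone: "Standardized radiographs will be taken at baseline and at the end of study at 9 months".

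Other sections lean towards change rather than final values. Study Purpose and Rationale describes the study used for sizing as showing "a significant reduction in probing depth in patients treated with a diode laser compared to those treated with standard scaling and root planing". Research Question(s)/Hypothesis(es) expects that "this will manifest with improved clinical parameters in subjects that receive this method of treatment".

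Patients are randomised and counted, so the patient is the implied unit. Study Design admits patients "with the presence of at least one implant presenting with early to moderate peri-implantitis" and defines the disease partly by "probing depths around the implant of 5- 8mm". No rule says how four sites, or several implants, become one value per patient.

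The one stated use of earlier readings is in Data and Safety Monitoring, where each patient's readings are checked against that patient's previous ones. That is within-patient safety surveillance, not a comparison of arms.

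**The concern.** A pre-treatment measurement of the outcome is usually the best available predictor of its later value. If it is left out, the part of the 9-month variation that was already present at baseline stays in the error term, and any chance imbalance between two arms of 13 stays in the estimate.

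The text also leaves open whether 9-month values or changes will be compared. In 26 patients the two can give different answers, and picking between them after seeing the data invites selection. What is at stake is the width of the confidence interval and a choice fixed in advance. Validity is not at stake.

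**Working it through.** **Inputs from the documents.** 13 per arm, difference 1.72 mm, SD 1.13 mm, alpha 0.05, power 90% (Statistical Procedures); depth at four sites at both visits (Study Procedures); entry depth 5 to 8 mm (Study Design).

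**Assumptions not in the documents.** Two-sided testing; patient-level SD; r = 0.3, 0.5 and 0.7; a common slope in both arms.

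**The plan's own figure.** Normal approximation: n = 2 × [(1.960 + 1.282) × 1.13 / 1.72]² = 9.07, so 10 per arm. The exact t-test has power 0.896 at 10 and 0.924 at 11, so it needs 11. The stated 13 is not reproduced but errs on the safe side: power at 13 per arm is 0.961.

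**Unadjusted interval.** Standard error = 1.13 × √(2/13) = 0.443 mm. With 24 df, t = 2.064, so the 95% half-width is 0.91 mm.

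**ANCOVA when 1.13 mm is the SD of 9-month values.** Variance relative to unadjusted = (1 − r²) × (1 + 1/22), where 1/22 is the average price of estimating the slope with 26 patients. Half-width = 2.069 (23 df) × 0.443 × √ratio.

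| r | variance ratio | change in variance | half-width, mm |
|---|---|---|---|
| 0 | 1.045 | +4.5% | 0.94 |
| 0.3 | 0.951 | −5% | 0.89 |
| 0.5 | 0.784 | −22% | 0.81 |
| 0.7 | 0.533 | −47% | 0.67 |

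Break-even on interval width, allowing for the lost df: (1 − r²) × (23/22) × (2.069/2.064)² = 1, which gives r ≈ 0.22.

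**How large r might be.** The entry range limits baseline spread. If patient baselines were uniform on 5 to 8 mm, their SD would be 3/√12 = 0.87 mm. The slope of 9-month on baseline depth is r × 1.13/0.87, so r = 0.7 needs a slope of 0.91. Slopes of 0.5 and 0.7 give r = 0.38 and 0.54, and variance cuts of about 11% and 26%. This is illustrative only: the plan does not say whether 5 to 8 mm refers to every site, the deepest site or a mean, so it may not describe a four-site mean.

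**ANCOVA when 1.13 mm is the SD of changes.** With equal SDs at both visits, variance relative to change scores = (1 − r²)(1 + 1/22)/(2 − 2r) = (1 + r)/2 × 23/22.

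- r = 0.3: 0.680, a cut of 32%
- r = 0.5: 0.784, a cut of 22%
- r = 0.7: 0.889, a cut of 11%

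With a baseline SD of 0.87 mm instead, the 9-month SD s solves s² − 2r(0.866)s + 0.866² = 1.13², giving s = 1.03, 1.28 and 1.55 mm. The ratio s²(1 − r²)(23/22)/1.13² is then 0.792, 1.003 and 1.006: a cut of 21%, then essentially nothing.

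**Bound on the loss.** Comparing 9-month values fixes the slope at 0; comparing changes fixes it at 1. The residual variance at the true slope is no larger than at either. Estimating the slope multiplies it by 1 + 1/22, so ANCOVA's variance exceeds that of either alternative by at most about 4.5%.

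**The case against.** The strongest case against is that the benefit is unproven and may be small. No r is given, and the narrow entry range may keep it modest. At r = 0.3 the half-width moves only from 0.91 to 0.89 mm, and in some change-score cases the gain is nil. Power at 1.72 mm is already about 96%, in a study that calls itself a pilot at feasibility phase. All of this stands, and it is why the claim is conditional. It does not remove the case for adjusting, because the possible loss is small and bounded while the possible gain is not. Nor is the sizing target the only effect of interest: at an illustrative 1.0 mm, power is about 58% unadjusted and 68% with ANCOVA at r = 0.5.

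A second objection is that the larger gap is the absence of any analysis. That also stands. A reader might infer that the plan has chosen an unadjusted test; it has chosen none. But some analysis must be written, and this is one sound form for it.

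Third, the evidence for a change-score intention is thin: one sentence about a different laser study and a general phrase in the hypothesis. The sizing sentence reads more naturally as 9-month values. The ambiguity is worth settling, and ANCOVA suits either intention.

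A reader might also infer that sites or implants are to be treated as independent. No passage proposes that; only the rule for summarising them is missing.

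**Conclusion.** The point holds in a limited form. Baseline probing depth is collected and has no stated role in the comparison of arms, because no analysis model is stated. Adjusting for it is likely to narrow the interval, but that rests on an r of more than about 0.22 if 1.13 mm is the SD of 9-month values. The plausible gain in variance is then about 5% to 22% (r = 0.3 to 0.5). The 47% at r = 0.7 is less plausible given the entry range. If 1.13 mm is the SD of changes, the gain over change scores runs from about 32% to nil. The worst-case loss is about 4.5% in variance.

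Three stronger conclusions are tempting and unsupported. The documents do not show that ANCOVA would certainly be more precise, since they give no correlation. They do not show inflated type I error, since an unadjusted comparison of randomised arms is valid. They do not show too few patients for the stated target, since 13 per arm exceeds the 11 that the t-test needs. This is a change that should be made, with medium confidence about the size of its benefit.

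**What to change.** Add to Statistical Procedures, before outcome data are examined:

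> Probing depth at 9 months is compared between arms by ANCOVA with arm and pre-treatment probing depth as terms. Each randomised patient contributes one value per visit: the mean of the four sites, averaged over that patient's study implants if there is more than one. Bone level at 9 months, by radiograph and by sounding where measured at both visits, is analysed in the same way with its own baseline.

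The four-site mean is one defensible summary. Another, such as the deepest site, is acceptable if named in advance and used at both visits. For bone level, this model gives the same arm effect as ANCOVA of the change, so it still addresses progression. The condition on sounding is needed because Study Procedures describes it before treatment but does not list it among the 9-month assessments.

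State also:
- whether 1.72 mm and 1.13 mm refer to 9-month values or changes, and on which per-patient summary;
- whether the test is two-sided;
- which list of primary outcomes applies. Study Design includes probing depth; the Scientific Abstract omits it and lists gingival index instead. The two must be reconciled. Bleeding on probing, which is in both lists, needs its own analysis, and this text does not settle how several primary outcomes share alpha.

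Cost: a few sentences and one degree of freedom, with no new data. At r = 0, with 1.13 mm as the SD of 9-month values, the half-width would be 0.94 mm instead of 0.91 mm, and the difference detectable with 90% power about 1.53 mm instead of 1.50 mm.

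### Do the printed sample-size inputs fail to support 13 patients per arm, and does it matter?

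*Combined protocol and SAP*

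**What the plan says.** The whole sample-size argument is in the Statistical Procedures section of the combined protocol and SAP.

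- Source: "Power calculation was done based on a study published by" the authors of a diode-laser study. The Study Purpose and Rationale section says that study showed "a significant reduction in probing depth in patients treated with a diode laser compared to those treated with standard scaling and root planing".
- Target: "To detect a difference of 1.72 mm (SD: 1.13mm) in probing depth at 9 months of follow-up".
- Result: "we will need 13 patients in each of control and test groups (at 90% power, and alpha of 0.05".
- Allocation: "The ratio of sample size in group 1 to group 2 is 1".

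Study Design gives the matching total: "This clinical study will involve 26 human subjects", which is 2 × 13. Two labels set the ambition of the trial. The Medical Device section has "Phase of Study: Feasibility", and the Research Question(s)/Hypothesis(es) section says "this will serve as a pilot study to explore possible differences".

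Four things are not stated anywhere: the test, whether it is one- or two-sided, whether 1.13 mm is a pooled or a one-arm SD (and of a 9-month value or of a change), and whether 13 includes an allowance for loss.

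**The concern.** A sample-size statement that prints a difference, an SD, a power, an alpha and a ratio looks complete, so a reader expects to recover the stated number from it. Here the usual calculation gives 11 per arm, not 13, and 13 per arm gives about 96% power, not 90%. The source compared two treated groups, yet a single SD is printed without a label, which raises the question of whether the right SD was used.

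The practical stake is loss to follow-up. Patients are followed for 9 months, and enrolment is exactly twice the number said to be needed. If 13 is the evaluable number required, there is no cushion. If 13 already contains a cushion, there is one. The text does not say which.

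**Working it through.** **Inputs from Statistical Procedures:** δ = 1.72 mm, SD = 1.13 mm, power 90%, α = 0.05, ratio 1, stated n = 13 per arm.

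**Assumptions added here, because the plan is silent:** 1.13 mm is the common between-patient SD, the test is a two-sample t-test, and nothing is added for loss.

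**Step 1. Try to reproduce 13.** The standardised difference is 1.72 / 1.13 = 1.522.

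Normal approximation, two-sided: n = 2 × [SD × (z₀.₉₇₅ + z₀.₉₀) / δ]² = 2 × [1.13 × (1.960 + 1.282) / 1.72]² = 9.07, so 10 per arm.

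Exact t-test: power comes from the noncentral t distribution with 2n − 2 degrees of freedom and noncentrality 1.522 × √(n/2).

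| n per arm | two-sided power | one-sided power |
|---|---|---|
| 9 | 85.8% | 92.6% |
| 10 | 89.6% | 94.8% |
| 11 | 92.4% | 96.4% |
| 12 | 94.5% | 97.5% |
| 13 | 96.1% | 98.3% |

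The smallest n reaching 90% is 11 two-sided. One-sided it is 9, since 8 gives 89.4%. The one-sided normal approximation gives 8. None of these four readings gives 13, and reading the test as one-sided only widens the gap.

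**Step 2. Size of the gap.** Under the two-sided t-test the requirement is 22 in total against 26 planned, a difference of 4. With 13 per arm, 90% power is reached at a difference of 1.50 mm rather than 1.72 mm. Alternatively, at 1.72 mm, 13 per arm keep 90% power up to an SD of 1.2976 mm, which is 1.2976 / 1.13 − 1 = 14.8% above the printed value.

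**Step 3. Which unstated choices would give exactly 13?** The first three keep every printed input.

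- Loss allowance on 11: 11 / 0.90 = 12.2 and 11 / 0.85 = 12.9, both rounding up to 13. Any loss rate above 1 − 11/12 = 8.3% and up to 1 − 11/13 = 15.4% does the same.
- Loss allowance of 20% on the normal-approximation figure: 10 / 0.80 = 12.5, so 13.
- Rank test with the worst-case efficiency of 0.864: 11 / 0.864 = 12.7, so 13.
- A common SD above 1.2417 and up to 1.2976 mm. If 1.13 mm belongs to one arm only, the other arm's SD would have to lie between √(2 × 1.2417² − 1.13²) = 1.344 mm and √(2 × 1.2976² − 1.13²) = 1.446 mm.
- 95% power, or a two-sided α of 0.025, with the t-test.

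The list is not exhaustive. The SD ranges were solved backwards from 13 and are not evidence of what was used. The cited study is not available here, so its SD cannot be checked.

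**Step 4. What if two patients per arm are lost?** With a common SD of 1.13 mm, 11 evaluable per arm give 92.4%. If the SD behind the calculation was 1.242 to 1.297 mm (assumed), 11 per arm give 87.0% down to about 84.1%.

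**The case for a change.** The strongest argument for acting is that the plan makes a formal 90% power claim, so its inputs should reproduce it. They do not, and several incompatible explanations fit equally well. The gap is also more than rounding: six percentage points of power and four patients. The pilot label does not excuse a calculation that is presented as a formal one. Step 4 gives the point some practical edge, because whether losing two patients per arm leaves power above or below 90% depends on information that is not printed. Correcting it would take one look-up and one sentence.

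The description stands: the statement is incomplete, and a reader cannot tell how 13 was reached. The inference that something needs changing does not stand. An arithmetic error would require knowing that a t-test was used, that 1.13 mm is the common SD and that nothing was added, and the plan says none of these. The least favourable case in Step 4 rests on an assumed SD and still leaves about 84% power, which is reasonable for a study that calls itself a pilot. Whichever explanation is true, the sensible course is to recruit 26. The planning SD does not enter the final comparison, whose precision will come from the observed data.

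**Conclusion.** No change to the plan follows. The printed inputs alone give 11 per arm, with 92.4% power, where the plan has 13, with 96.1%. This is conditional on a common SD of 1.13 mm, a two-sided two-sample t-test and no loss allowance. On that reading the plan has spare power. On the other readings examined, 13 is the correct answer to a calculation that was only partly reported. An ordinary 10% or 15% allowance on 11 is enough to explain it.

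This is missing detail whose recovery gains nothing for the trial: 26 patients would still be enrolled, followed for the same 9 months and compared in the same way. When the results are written up, the test, its sidedness, the meaning of the SD and any allowance can be stated from the original calculation. It would be wrong to replace 90% with 96% unless all three conditions above are confirmed, and equally wrong to cut enrolment to 22. The conclusion covers only whether 13 per arm is adequate for the stated 1.72 mm difference. It does not address whether that difference is a realistic target, or how the outcomes should be analysed.
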